## **Impact of Fenugreek Supplementation on Obesity and Hyperglycemia among Diabetic Adults in Saudi Arabia: A Quasi-Experimental Study**

Overweight and obesity are major global public health concerns associated with negative impacts on quality of life, increased morbidity, and higher mortality rates. Overweight refers to a state of excessive fat accumulation, while obesity is defined as a chronic, complex disease characterized by excessive fat deposits that impair health. Overweight is defined as a BMI ranging from 25 to 29.5, while obesity is defined as a BMI equal to or greater than 30 [1, 2].

Overweight and obesity are estimated to be the fifth leading cause of premature death. The WHO reported that one in eight people worldwide were living with obesity in 2022. Moreover, 2.5 billion adults were classified as overweight, with 890 million of them living with obesity. Overall, 43% of adults were overweight, and 16% were obese [2, 3–6].

The number of obese individuals has almost tripled since 1975. By 2025, obesity is expected to surpass 18% in men and 21% in women. Furthermore, the World Obesity Atlas predicts that by 2035, more than half of the world's population will be overweight or obese. These statistics highlight the urgent need for comprehensive public health strategies to address the rising prevalence of obesity across all age groups [2, 3–7].

As obesity reaches epidemic proportions globally, people in the Gulf countries have also been significantly affected, particularly in high-income, oil-producing nations. The prevalence of obesity in Gulf countries ranges from 2% to 55% among adult females and from 1% to 30% among adult males [8].

Overweight and obesity are associated with numerous chronic health conditions such as cardiovascular, respiratory, and gallbladder diseases, as well as Type 2 Diabetes Mellitus (T2DM), hypertension, certain types of cancer, osteoarthritis, and asthma. These conditions increase the burden on healthcare systems and reduce life expectancy [8–10].

T2DM is a chronic metabolic disorder marked by elevated blood glucose levels (hyperglycemia) and glucose intolerance, primarily due to the body's diminished sensitivity to insulin. This impairment triggers increased insulin production, which can eventually lead to insulin deficiency. In 2021, the global prevalence of T2DM among individuals aged 20 to 79 was 10.5%, with projections indicating a rise to 12.2% by 2045 [11–13].

T2DM is commonly associated with a cluster of conditions including high blood sugar, insulin resistance, dyslipidemia, hypertension, and obesity, which often occur together. The development of T2DM is influenced by a combination of genetic, environmental, and behavioral factors. As such, addressing this complex condition requires integrated strategies to manage the interconnected health issues it involves [11–13].

In recent years, conventional medical therapies for obesity have shown limited effectiveness. Evidence suggests that obese patients increasingly turn to alternative remedies in an effort to lose weight. These remedies include nutritional medicinal plants such as Fenugreek, which is one of

the oldest and most widely used herbs due to its safety, affordability, availability, and ease of use [3, 14–18].

Fenugreek has demonstrated medicinal and nutritional benefits. It has been used to reduce body weight and manage metabolic complications, as it contains essential active ingredients (e.g., flavonoids, fiber, alkaloids, and amino acids) that reduce intestinal absorption of carbohydrates and improve glucose regulation in the liver and muscle tissue. It also possesses antidiabetic, antibacterial, anticancer, antioxidant, and anti-anorexic properties [16, 19–21].

Additionally, Fenugreek may act as an appetite suppressant by increasing the levels of cholecystokinin and glucagon-like peptide-1 hormones, which are involved in regulating appetite. When added to carbohydrate-containing meals, its high fiber content enhances the sensation of fullness among overweight or obese individuals, leading to reduced food intake and weight loss [21, 22].

Fenugreek may also increase insulin sensitivity by enhancing the insulin signaling pathway through upregulation of insulin receptors, thereby promoting glucose uptake and reducing postprandial blood glucose levels. Its amino acid content (notably 4-hydroxyisoleucine) stimulates insulin release and helps regulate blood sugar, ultimately reducing food cravings and promoting weight loss. Therefore, Fenugreek has proven beneficial for patients with diabetes or insulin resistance, as it reduces the blood sugar response to carbohydrate meals [23–25].

Moreover, Fenugreek has been shown to reduce fat absorption in the intestines and promote the breakdown of fat cells. Adding Fenugreek seed extract to a high-fat diet can improve glucose markers and lipid metabolism, resulting in weight loss and reduced body fat accumulation [26].

Fenugreek may also elevate levels of testosterone and adiponectin hormones. Testosterone is associated with increased skeletal muscle mass, which is essential for glucose clearance and accounts for over 80% of glucose uptake after meals. Adiponectin, on the other hand, may induce fat and weight loss by enhancing glucose utilization and fatty acid oxidation in peripheral tissues [27, 28].

Recent meta-analyses have shown that Fenugreek supplementation significantly improves glycemic control by reducing FBS and HbA1c, enhancing insulin sensitivity, supporting weight loss, and improving lipid profiles. These effects may contribute to reducing complications, lowering healthcare costs, and supporting Saudi Arabia's Vision 2030 health goals [7, 29, 30].

Overall, Fenugreek presents a promising and culturally appropriate intervention for managing T2DM and obesity in the region. This study is of considerable importance in addressing the increasing prevalence of T2DM and obesity within Saudi Arabia. As a traditional herbal remedy, Fenugreek has garnered attention for its potential therapeutic effects on metabolic disorders [7, 30].

The significance of this study also lies in the potential impact of Fenugreek supplementation on managing obesity and hyperglycemia among diabetic adults in Saudi Arabia—a country with some of the highest rates of diabetes and obesity worldwide [31].

As of 2024, the prevalence of obesity among Saudi adults ranges from 20% to 39%. Common obesity-related complications include hypertension (67.6%), T2DM (60.7%), and hypercholesterolemia (51.3%). There is a well-established link between rising BMI and increased risk for these health conditions. Additionally, the economic burden of obesity in Saudi Arabia is substantial, with treatment and management costs estimated at around 6.4 billion US dollars [31].

In Saudi Arabia, where obesity and T2DM are prevalent due to lifestyle factors, Fenugreek offers a culturally suitable and cost-effective dietary intervention. Investigating its effects on obesity and glycemic control could support its inclusion in national health strategies and the development of comprehensive treatment plans that integrate both medical and non-medical approaches [31, 32].

This study aims to address the existing research gap by generating region-specific evidence on the effectiveness of Fenugreek supplementation. The findings will support evidence-based practice and inform public health policies tailored to the Saudi population. Ultimately, the study seeks to improve health outcomes, ensure patient safety, and reduce morbidity and mortality among adults with diabetes and obesity.

#### Aim of the study

This study aimed to examine the impact of Fenugreek supplementation on obesity and hyperglycemia among diabetic adults in Hail city, Saudi Arabia

#### Research hypotheses

H1: Diabetic adults who consume Fenugreek supplementation exhibit less BMI will be compared to those who do not consume it.

H2: Diabetic adults who consume Fenugreek supplementation exhibit lower blood glucose levels will be compared to those who do not consume it.

## 2. Materials and Methods

### Study design

A quasi-experimental research design (pretest-posttest nonequivalent control group design) will be adopted in this study.

### Study settings

This study will be conducted at the diabetic clinics affiliated to Diabetes and Endocrine Center, University medical clinics and King Khalid hospital in Hail city, Saudi Arabia. These settings will be selected because of their higher turnover of diabetic cases, which will be satisfactory for the study.

### Study participant

---

A convenience sample of 80 participants will be recruited from the aforementioned settings using a non-probability sampling technique. Eligible participants will include male and female adults over the age of 22 who are either overweight (BMI ranging from 25 to 29.5 kg/m^2) or obese (BMI exceeding 30 kg/m^2). All participants must have a confirmed diagnosis of Type 2 Diabetes Mellitus (T2DM), be cognitively able to participate in the study, and express a willingness to do so. However, individuals with diabetes who are undergoing insulin therapy, pregnant or breastfeeding women, and those suffering from chronic diseases other than T2DM will be excluded from the study.

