#### Intervention Procedures

Participants will be equally divided into two groups: a study group and a control group, each comprising 40 individuals. Following the provision of informed consent, participants will be randomly assigned to either the study group—which will receive Fenugreek supplementation in addition to standard care—or the control group, which will receive standard care alone. Randomization will be performed using a computer-generated random number list to ensure unbiased allocation.

Due to the practical challenges associated with dietary interventions and the absence of placebo controls in this setting, blinding will not be feasible for participants or the researchers administering the intervention. Consequently, participants will be aware of their group assignments. Nonetheless, outcome assessors and data analysts will remain blinded to group allocation throughout the data collection and analysis phases to minimize detection and performance biases.

Participants in the study group will continue their prescribed anti-diabetic treatment and adhere to a standardized dietary plan, in addition to consuming Fenugreek seed powder (10 g in sachet form) daily before breakfast and dinner for a duration of three months. In contrast, the control group will receive only their prescribed anti-diabetic treatment while following the same dietary plan. To enhance adherence to the intervention, researchers will maintain weekly telephone contact with participants in the study group, emphasizing the importance of compliance with both the Fenugreek supplementation and dietary plan.

Upon completion of the three-month intervention, a comparative analysis will be conducted between the study and control groups to evaluate the impact of Fenugreek supplementation on obesity and hyperglycemia in adults with T2DM.

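### The hypotheses compare fenugreek consumers with non-consumers, but current users may enrol and the protocol lists no item recording fenugreek use in either arm, so any own use would shrink the contrast unseen.

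*Protocol*

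**What the plan says.** Research hypotheses defines the contrast by consumption. H1 reads "Diabetic adults who consume Fenugreek supplementation exhibit less BMI will be compared to those who do not consume it", and H2 reads "Diabetic adults who consume Fenugreek supplementation exhibit lower blood glucose levels will be compared to those who do not consume it".

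The exclusions under Study participant are these: "individuals with diabetes who are undergoing insulin therapy, pregnant or breastfeeding women, and those suffering from chronic diseases other than T2DM will be excluded". Neither current nor recent fenugreek use is among them, and no washout is set.

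Data collection lists age, gender, BMI, FBS, RBS and HbA1c. BMI, FBS and RBS are taken at baseline and at one, two and three months, HbA1c at baseline and three months. Fenugreek intake is not listed at any of these times.

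Under Intervention Procedures, "the control group will receive only their prescribed anti-diabetic treatment while following the same dietary plan". Participants know their assignment. For adherence, "researchers will maintain weekly telephone contact with participants in the study group"; no such contact is described for controls.

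The introduction describes fenugreek as one of "the oldest and most widely used herbs due to its safety, affordability, availability, and ease of use", and says: "Evidence suggests that obese patients increasingly turn to alternative remedies in an effort to lose weight".

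**The concern.** The hypotheses need a comparator that does not take fenugreek, and nothing in the protocol secures or checks one. An existing user who meets the other criteria is eligible and can be randomised to either arm. A control participant knows which product is being tested and, on the protocol's own description, can obtain it easily and cheaply.

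What is at stake is how the result can be read. If some controls take fenugreek, the comparison by assigned group estimates something smaller than the contrast in H1 and H2. With no intake item among the listed data, a small or null difference could not be separated from a comparator that was partly exposed, and no later analysis can recover use that was not recorded. Eligibility and data items belong in a protocol, so this is not a matter that a statistical analysis plan could settle.

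**Working it through.** **1. The plan's own figure.** Sample size gives a population of N = 416, expected frequency p = 0.5, margin 0.10 and 95% confidence (z = 1.96). The finite-population formula for one proportion is n = N·p(1 − p) / [(0.10/z)²·(N − 1) + p(1 − p)] = 416 × 0.25 / [(0.10/1.96)² × 415 + 0.25] = 78.18. This reproduces the stated 78, raised to 80. The formula contains no effect size and no between-group comparison, so it makes no allowance for fenugreek use outside the trial.

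**2. Use by controls during the trial.** Let δ be the effect with no outside use, c the share of controls who take fenugreek, and e their exposure as a fraction of full effect (0 to 1). The control mean moves by c·e·δ, so the difference becomes δ(1 − c·e). At full exposure (e = 1) this is δ(1 − c).

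**3. Users already taking it at entry.** Randomisation spreads them over both arms. Suppose a share c in each arm already has the full effect, keeps using, and gains nothing more from the trial product.
- Final values: the study arm is shifted by δ and the control arm by c·δ. The difference is δ(1 − c).
- Change from baseline: the study arm changes by (1 − c)δ and the control arm by 0. The difference is again δ(1 − c).

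This is one loss, seen on two scales. It depends on a ceiling: if the trial product adds its full effect on top of prior use, prior users cause no shrinkage.

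**4. Power.** Intervention Procedures gives 40 per arm and Statistical analysis gives a 5% level; two-sided testing is assumed. The protocol states no effect size, SD, power or rate of use, so all of these are assumptions. With a two-sample t-test, δ = 0.634 SD gives 80% power and is taken as the starting point.

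| Share of controls using (c) | Effect, full exposure | Power, full exposure | Effect, half exposure | Power, half exposure |
|---|---|---|---|---|
| 0% | 0.634 | 80% | 0.634 | 80% |
| 10% | 0.571 | 71% | 0.602 | 76% |
| 20% | 0.507 | 61% | 0.571 | 71% |
| 30% | 0.444 | 50% | 0.539 | 66% |

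At a quarter of full exposure, power is about 78%, 76% and 74% for 10%, 20% and 30% use.

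**5. Other starting effects, full exposure, c = 0%, 10%, 20%, 30%.**
- 0.5 SD: 60%, 51%, 42%, 34%.
- 0.8 SD: 94%, 89%, 81%, 70%.

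**6. Sample size.** At full exposure, the number needed to restore the same power grows by 1/(1 − c)²: 1.23, 1.56 and 2.04 times for 10%, 20% and 30% use.

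**The case against.** The best defence is that the control condition is already specified. Controls get only their prescribed treatment and the shared dietary plan, which implies no fenugreek. That wording describes what is provided. It does not tell controls to avoid fenugreek or check whether they do, the content of the dietary plan is not given, and it cannot deal with use before enrolment.

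A second defence is that Intervention Procedures and Expected Outcomes describe the comparator as standard care, and a comparison by assignment that tolerates background use is a legitimate question. That is true, but H1 and H2 are worded against non-consumers. Even under the standard-care reading, use has to be recorded for the result to be interpretable.

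Third, the interview tool is described in general terms and is not shown, so it may ask about herbal intake. This stands in part: one can say only that intake is not among the listed items.

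Fourth, the introduction's remarks are general and do not concern patients at the Hail clinics or use at trial-like exposure. This stands in full. A reader might infer that the effect is certainly diluted, or that control-arm use is likely. The documents give no rate of use and support neither statement. A reader might also infer that prior users cost the trial twice, once in each arm; step 3 of the working shows a single loss, and only under a ceiling.

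**Conclusion.** The concern holds in conditional form. Eligibility and the listed data do not secure or verify the non-consuming comparator that H1 and H2 require. If participants use fenugreek on their own, the between-group difference shrinks by a factor of up to (1 − c), less at lower exposure, and the listed data would not show it.

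The direction is sound; the size is unknown. The fall from 80% to about 71%, 61% or 50% is an illustration that rests on an assumed 0.63 SD effect, assumed shares of use, full exposure in those who use, and two-sided testing. Casual use would cost less, and with a 0.8 SD effect even 20% full-exposure use leaves about 81%. The point still merits a change, because the remedy is small and unrecorded use cannot be recovered afterwards.

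**What to change.** - **Study participant:** add current regular use of fenugreek or of a product containing it to the exclusions.
- **Data collection:** add one question on fenugreek use outside the trial, asked in both arms at baseline and at months 1, 2 and 3, which are already measurement times.
- **Reporting and analysis:** report the answers by assigned group, and keep the main comparison by assigned group.

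The two parts do different work. The exclusion removes existing users at entry but does not stop use that starts during the trial; the question would record that use.

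The cost is one exclusion line, one interview item and some lost candidates. How many cannot be told from the protocol: the 416 per month under Sample size is the population entered in a survey formula, not the flow of eligible patients, and the existing exclusions for insulin therapy and other chronic disease already reduce that pool.

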#### Sample size

---

The Epi Info 7 statistical program were used to estimate the appropriate sample size for this study, based on the following parameters: a population size of 416 participants per month, an expected frequency of 50%, a margin of error of 10%, and a confidence level of 95%. According to these calculations, the minimum required sample size is determined to be 78 participants. To account for potential non-response and to ensure adequate representation, the final sample size will be increased to 80 participants.

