#### Data collection

Data will be collected from each participant through an individually administered interview schedule. The structured interview tool, developed by the researchers, will be designed to gather both personal and clinical data relevant to the study. Personal data will include participants' age (in years), gender, and Body Mass Index (BMI), which will be calculated using the following equation:

$$\text{BMI} = \text{weight (kg)} / \text{height}^2 (\text{m}^2).$$

Weight will be measured in kilograms (kg) using a calibrated scale, with participants wearing minimal clothing and no shoes. Height will be measured in meters (m) using a stadiometer, with participants standing upright on a flat surface (neither slumping nor stretching), barefoot, and with their heels, shoulders, and the back of the head aligned vertically, looking straight ahead without tilting the head up or down [33, 34].

Clinical data will include:

Fasting Blood Sugar (FBS) in mg/dL,

Random Blood Sugar (RBS) in mg/dL, and

Glycated Hemoglobin (HbA1c) in percentage (%).

BMI, FBS, and RBS will be measured at four time points: baseline, and at one, two, and three months. HbA1c will be assessed at two time points: baseline and at three months.

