#### Statistical analysis

The collected data will be carefully categorized, coded, computerized, tabulated, and will be analyzed using the Statistical Package for Social Sciences (SPSS) version 23 program. To explore the relationships between the study variables, cross-tabulation will be performed, which will be a standard and appropriate approach for identifying associations and distributions of categorical data.

Comparisons between groups of categorical variables will be conducted using the Chi-square test (Monte Carlo). This test will be particularly useful when expected frequencies will be low, and thus, its use here will be well-justified. For comparisons involving two categories of normally distributed quantitative variables, the Student's t-test will be employed, which will be the conventional choice for assessing mean differences between two independent groups.

Additionally, to compare the three repeated measurements (baseline, one, two, and three months) within each group, analysis of variance (ANOVA) with repeated measures will be conducted, followed by Bonferroni adjustment to control for multiple comparisons. The application of partial Eta squared will be appropriate for determining the effect size of the intervention, thus providing insights into the magnitude of observed differences. Throughout the analyses, a 5% significance

level will be used to judge the statistical significance of the results, aligning with the standard threshold in clinical research.

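### The stated minimum of 78 is a survey size for estimating one proportion, so it is not a minimum for the 40-versus-40 comparison of means that the trial makes

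*Protocol*

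**What the plan says.** The Sample size section names Epi Info 7 and lists its inputs as "a population size of 416 participants per month, an expected frequency of 50%, a margin of error of 10%, and a confidence level of 95" per cent. It concludes that "the minimum required sample size is determined to be 78 participants", and then adds: "To account for potential non-response and to ensure adequate representation, the final sample size will be increased to 80 participants".

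Other sections of the Protocol describe the study that this number is meant to serve:

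- Study participant: "A convenience sample of 80 participants will be recruited from the aforementioned settings using a non-probability sampling technique".
- Intervention Procedures: "Participants will be equally divided into two groups: a study group and a control group, each comprising 40 individuals". Assignment is random, and the groups are compared after three months.
- Data collection: "BMI, FBS, and RBS will be measured at four time points"; HbA1c is measured at baseline and three months. All four outcomes are continuous.
- Research hypotheses: H1 (BMI) and H2 (blood glucose) are both between-group statements. H2 begins "Diabetic adults who consume Fenugreek supplementation exhibit lower blood glucose levels", set against those who do not take it.
- Statistical analysis: the between-group test for quantitative variables is Student's t-test, described as "the conventional choice for assessing mean differences between two independent groups", at the 5% level. The chi-square test is for categorical variables, and the repeated-measures ANOVA is run within each group.

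**The concern.** An expected frequency, a margin of error and a population size are the inputs of a prevalence survey. They fix the width of a confidence interval around one proportion in one population. The Protocol plans no such estimate. The size needed for a two-arm comparison of means depends on the difference sought, the SD, the significance level and the power, and three of those four are absent from the calculation.

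This is more than an omission that a statistical analysis plan could fill. The Protocol gives a complete calculation and draws from it a conclusion, a minimum required size, that does not follow for this design. It is also the only basis given for the number of participants. If the trial finds no difference, a reader would think that it had met a calculated minimum, when nothing in the calculation says what 40 versus 40 could detect.

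The survey formula has a second mismatch: it presumes a probability sample from the population of 416, whereas the trial takes a convenience sample.

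**Working it through.** **1. Reproducing the Protocol's figure.** Inputs from the Sample size section: population N = 416, p = 0.50, margin d = 0.10, 95% confidence (z = 1.96).

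- Before finite-population correction: n0 = z²p(1−p)/d² = 3.8416 × 0.25 / 0.01 = 96.04.
- After correction: n0 / [1 + (n0 − 1)/N] = 96.04 / (1 + 95.04/416) = 78.18.
- Variant correction: n0 / (1 + n0/N) = 96.04 / (1 + 96.04/416) = 78.03.

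Both agree with the stated 78. The arithmetic is right, and it identifies the formula as the one for a single proportion.

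**2. What moves the 78.** The same formula with other survey inputs, chosen here for illustration:

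| Population | Margin | n |
|---|---|---|
| 416 | 5 points | 199.97, about 200 |
| 416 | 10 points | 78.18 |
| 416 | 15 points | 38.80, about 39 |
| 3 × 416 = 1248 | 10 points | 89.24, about 89 |

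None of these changes alters the power for H1 or H2 at a given number per arm.

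**3. What the trial's own comparison needs.** Two-sample t-test (noncentral t), 1:1 allocation, 5% level. Two-sided testing is an assumption, since the Statistical analysis section does not state sidedness. The Protocol gives no difference or SD, so the standardised differences below are an assumed range.

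| Difference (SD) | Per arm for 80% power | Total | Power at 40 per arm |
|---|---|---|---|
| 0.8 | 26 | 52 | 94% |
| 0.6 | 45 | 90 | 75% |
| 0.5 | 64 | 128 | 60% |
| 0.4 | 100 | 200 | 42% |

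**4. Difference detectable with 80% power.**

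- 40 per arm: 0.634 SD.
- 36 per arm (illustrative 10% loss): 0.670 SD.
- 32 per arm (illustrative 20% loss): 0.711 SD.

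At 39 per arm, a total of 78, it is 0.643 SD. So 78 is the 80%-power requirement only if the target is about 0.64 SD, and the Protocol names no such target.

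**5. The step from 78 to 80.** (80 − 78)/80 = 2.5%. Two participants are added to a survey size, in terms of non-response and representation. This preserves the precision of the survey estimate, not the power of the comparison.

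**The case against.** The best counter-arguments accept that the formula does not match and dispute how much follows.

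- *Eighty may be enough.* That is so. Nothing here shows 80 to be too few. Equally, keeping 80 does not make it adequate, and a detectable difference worked back from 80 describes the trial without justifying its size. That is why the sponsor must state its actual basis.
- *The SD is ambiguous.* The design is pretest-posttest, and the Statistical analysis section does not say whether the t-test is applied to three-month values or to changes from baseline. This stands as a point of wording: 0.63 SD means the SD of whichever variable is tested. For a t-test on change, the equivalent in cross-sectional SDs is 0.634 × √[2(1 − r)], which gives 0.75 at an assumed baseline correlation r of 0.3, 0.63 at 0.5, 0.49 at 0.7 and 0.28 at 0.9. The replacement text should therefore say which SD is meant.
- *The section speaks of non-response, not dropout, and makes no power claim.* That is correct. The 2.5% should not be read as a planned dropout rate. But calling 78 a required minimum for this study is still a claim about its size that the calculation does not support.
- *Some of the ranges are chosen, not given.* The alternative margins, the 1248, the 0.4 to 0.8 SD range and the loss rates are all illustrative. The main point rests on none of them.
- *The consequence is small, since conduct does not change.* The fix is cheap, but the paragraph is the only justification for the sample size and it applies to neither hypothesis.

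**Conclusion.** The concern holds and should be corrected. The 78 is correctly computed for a question that the trial does not ask, and its description as a required minimum is unsupported for H1 and H2. No corrected sample size can be computed, because the Protocol gives no target difference, SD or power. What can be said is conditional: with 40 per arm, a two-sided 5% t-test, no loss, no baseline adjustment and each outcome taken singly, power reaches 80% at about 0.63 SD of the analysed variable and falls below that for smaller differences. Adjustment for baseline would raise power; a multiplicity adjustment across the four outcomes would lower it.

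**What to change.** Keep 80 participants. In the Sample size section, delete the survey calculation, the claim of a minimum of 78 and the sentence that raises 78 to 80. Replace them with text such as:

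> 80 participants, 40 per arm. [The sponsor states its actual basis for 80: a target between-group difference with SD and power, or feasibility.] For each outcome taken singly, 40 per arm gives 80% power at two-sided 5% for a difference of about 0.63 SD of the analysed variable [three-month value or change from baseline, to be named] with the Student's t-test of the Statistical analysis section (0.67 SD if 36 per arm complete, 0.71 SD if 32, as illustrative loss scenarios).

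Three conditions go with it:

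- If the sponsor names a target below about 0.63 SD, state the actual power at 80 (75% at 0.6 SD, 60% at 0.5 SD, 42% at 0.4 SD) and do not claim 80%.
- Convert SDs to clinical units only with SDs sourced from the sponsor's own clinics or from cited data, and for the same variable that is tested.
- Give baseline-adjusted figures only if the Statistical analysis section is changed to adjust for baseline. In that case show the whole range from 0.634 × √(1 − r²): 0.605 SD at r = 0.3, 0.55 at 0.5, 0.45 at 0.7 and 0.28 at 0.9.

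The cost is one rewritten paragraph, with no extra participants and no change to conduct. The stated justification will look less favourable, because the sponsor must say openly whether 80 rests on a target difference or on feasibility.
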